10 STUDY MATERIALS

10.1 STUDY PRODUCT

10.1.1 INVESTIGATIONAL PRODUCT FORMULATION AND DESCRIPTION

NOX66 is idronoxil formulated in two strengths in a proprietary lipophilic base to yield suppositories with a nominal weight of 2.2 or 3.3 g containing either 400 or 600 mg drug substance, respectively.

10.1.2 INVESTIGATIONAL PRODUCT PRESENTATION, STORAGE AND HANDLING

NOX66 is packaged with each suppository individually sealed in plastic packaging and boxed as quantities to meet the need of the treatment cycles under investigation. The drug product is stored refrigerated (2 – 8 °C). For each treatment period and cycle, the appropriate number of suppositories will be dispensed with at least enough for 1 extra day of treatment to account for misplaced or lost study drug.

10.1.3 INVESTIGATIONAL PRODUCT LABELLING

NOX66 suppositories will be packaged by the Sponsor and supplied in an open label basis. The primary plastic container which contains the suppository units will be labelled as follows: 1) Sponsor's name and address, 2) Study number, 3) Name of the product, 4) Lot Number, 5) Re-assay date, 6) Storage conditions, 7) Dosage and 8) Caution Statement: "New Drug--Limited by Federal (or United States) law to investigational use." The plastic container will be packaged in a box.

10.1.4 DOXORUBICIN, GROWTH FACTORS, DEXRAZOXANE

For details on doxorubicin see Section 8.2. The use of growth factors and dexrazoxane is permitted to reduce myelosuppression and cardiac toxicity due to doxorubicin. Growth factors may be used to treat neutropenia and thrombocytopenia in all cycles in the Dose Escalation and Expansion Cohorts (except for Cycle 1 in the Dose Escalation Cohorts). The degree of myelosuppression may be increased at Cycles 5 and 6 with the use of dexrazoxane. Doxorubicin should be given within 30 minutes after beginning the infusion with dexrazoxane. [Note: For breast cancer patients, dexrazoxane is recommended when doxorubicin cumulative dosage is $\geq 300 \text{ mg/m}^2$].

These products will be obtained as standard of care and are prescribed based on the Investigator's clinical judgement.

10.2 INVESTIGATIONAL PRODUCT ADMINISTRATION

10.2.1 ADMINISTRATION

Depending on the cohort/dose level, 2 to 3 suppositories will be self-administered daily for 7 days in the Monotherapy period (only for Dose Escalation part) and/or in combination with doxorubicin for the treatment cycles. In this study, the dosage forms will be inserted rectally either twice (12 hours apart) or three times (8 hours apart) per day. In patients who have regular bowel movements (i.e. within several hours after awakening) patients will be instructed to insert the suppository after the bowel movement. To promote regular movements, patients should be encouraged to consume a high fiber diet, with adequate amounts of water. In those patients who are not on a regular bowel movement schedule, insertion of the suppository should occur at regularly scheduled times individualized for the patient. If defecation occurs after NOX66 administration, no re-dosing is required. The next dose should be administered at the scheduled time. During the NOX66 and doxorubicin combination treatment cycles, if diarrhea occurs, the Investigator must follow standard management practices to manage the diarrhea to allow for NOX66 administration.

If any patients have difficulty with administering suppositories three times per day (8 hours apart) due to any personal reasons, dosing schedule can be changed to two times daily (3 suppositories per day) after Cycle 2. In this instance, patients can administer one 600-mg suppository in the morning and two 600-mg suppositories in the evening. While two suppositories are administered, each suppository needs to be inserted at least 5 minutes apart.

The dosing time for each suppository must be recorded by the patient in a diary which must be brought to the clinic at each visit. The dose escalation scheme is presented in [Table 1](#)

Proposed Starting Dose and Dose Escalation Scheme for NOX66

Table 1 Proposed Starting Dose and Dose Escalation Scheme for NOX66

Cohort	1	2	3
Increment	NA	50%	50%
Total daily dose (mg)	800	1200	1800
Daily regimen (mg)	400 BID	600 BID	600 TID

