	
 • Complete blood count • Electrolytes (Ca⁺⁺, Mg⁺⁺), PO₄, BUN, creatinine 
The following criteria will be used to evaluate the efficacy of NOX66 alone and in combination with doxorubicin:
 
 • RECIST v1.1: Disease Control Rate (DCR) defined as [(stable disease (SD) + partial response (PR) + complete response (CR)/All)], overall response rate (ORR) • Overall survival (OS), Progression Free Survival (PFS) • European Organization for Research and Treatment of Cancer: Core Quality of Life Questionnaire v3.0 (EORTC QLQ-C30) • Fatigue Severity Scale (European Organisation for Research and Treatment of Cancer: Cancer Related Fatigue Module - EORTC QLQ-FA12) • Brief Pain Inventory (short form) • Suppository Acceptance Questionnaire 
The following criteria will be used to evaluate the PK of idronoxil and metabolites in blood plasma after single and repeated doses of NOX66:
 
 • Maximum concentration (C_{max}) • Time to reach maximum concentration (T_{max}) • Trough concentrations after repeated administration • Area under the concentration-time curve up to last measurable time point and infinity (AUC_{last} and AUC_{inf}) • Area under the concentration-time curve over a dosing interval after repeated administration (AUC_T) • Terminal elimination half-life (if possible) 
Pharmacokinetic parameters of idronoxil and metabolites obtained on Day 7 will be compared to Day 1 values. Sparse PK sampling for determination of idronoxil and metabolites, doxorubicin and doxorubicinol concentrations will be obtained during the treatment cycles to assess variability of exposure of idronoxil and doxorubicin in an exploratory manner.
 
The following biomarkers will be evaluated to assess the relationship between response to NOX66 and doxorubicin:
 
 • Genetic mutations • Change in lipid profile from baseline • Cytokine/chemokine and ENOX2 dynamics
Number of Patients (Planned)	Up to approximately 34 patients with metastatic soft tissue sarcoma will be studied if the MTD is determined with the maximum dose planned for this study. If a minimum number of patients is studied per dose escalation, the expected number of patients is approximately 28.

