11.1.2 SECONDARY ENDPOINTS

11.1.2.1 Pharmacokinetics

Blood concentrations of idronoxil and idronoxil metabolites and plasma concentrations of doxorubicin and doxorubicinol will be assayed by validated methods by a central laboratory. PK parameters of idronoxil and metabolites, will be determined using non-compartmental analyses after administration of idronoxil on Days 1 and 7 during monotherapy in the Dose Escalation Part and include:

- C_{\max} Maximum observed blood drug concentration
- T_{\max} Time to reach C_{\max}

- AUC_{last} Area under the blood concentration time curve (AUC) from time 0 to the last measurable concentration
- AUC_{τ} AUC from time 0 to end or dosing interval (τ)
- AUC_{inf} AUC from time 0 to infinity (if possible)
- kel^a Terminal elimination rate constant, calculated from a semi-log plot of the blood concentration versus time. The parameter will be calculated by linear least squares regression analysis using the maximum number of points in the terminal log-linear phase (e.g., 3 or more nonzero blood concentrations).
- $T_{1/2a}$ Terminal elimination phase half-life, calculated as $0.693/kel$ (if possible)

^aNote: No value for kel, or $T_{1/2}$ will be reported for cases that do not exhibit a terminal log linear phase in the concentration versus time profile. Additional blood PK parameters may be calculated if deemed appropriate.

For the Dose Escalation Part, during the combination cycles, 1 to 4 PK samples will be obtained on Days 2, 7, and 8 to assess concentrations of idronoxil and metabolites or doxorubicin and doxorubicinol. For the Dose Expansion Part, 1 to 3 PK samples will be obtained on Days 2 and 7 to assess concentrations of idronoxil and metabolites or doxorubicin and doxorubicinol. Comparisons will be made to assess the degree of inter-and intra-patient variability during the study.

At the discretion of the Sponsor, non-evaluable concentrations or parameters may be excluded from the final PK analysis dataset. Any data exclusions will be documented in the final study report. The relationship between PK parameters and adverse events and other safety findings will be explored.

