14.3 STATISTICAL METHODOLOGY

14.3.1 GENERAL STATISTICS METHODS

All data will be summarized by idronoxil dose group. For safety analyses, a summary group consisting of all dose groups combined may also be presented.

For all measurements, the baseline value will be the last measurement taken before the first dose of study drug, whether idronoxil or of idronoxil + doxorubicin depending on the cohort.

Standard summary statistics will be presented for all measurements. For continuous variables, the standard summary statistics will be the number of observations (n), mean, standard deviation, median, minimum and maximum. For categorical variables, the standard summary statistics will be the number and percentage of observations in each category. Categories that are specified on the eCRF which contain no observations will be presented in the data summaries with a value of 0.

An AE with a completely missing start date will be assumed to start one minute after the date-time of the first idronoxil dose. If the severity of a reported AE is missing, it will be assumed that the event is severe; similarly, if the relationship of a reported AE to study treatment is missing, it will be assumed that the event is definitely related to treatment. No other missing data will be imputed. Incomplete start dates for Adverse Events and Concomitant Medications and incomplete end dates for AEs will have missing parts imputed by a conservative procedure which will be specified in the Statistical Analysis Plan (SAP).

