14.3.9 PHARMACOKINETIC ANALYSES

Blood concentration of idronoxil and metabolites will be summarized by collection time for each dose group using descriptive statistics. Separate summaries will be provided for idronoxil blood concentrations collected on Days 1 and 7 of idronoxil monotherapy, and from pre-dose to 4 hours post dose on Day 2 of Cycles 1 to 6. Trough values will also be assessed on Days 7 and 8 of Cycles 1, 3 and 5. Blood concentrations of idronoxil after monotherapy and in combination with doxorubicin will be compared.

Plasma concentrations of doxorubicin and doxorubicinol will be summarized by collection time for each dose group using descriptive statistics.

Pharmacokinetic parameters will be summarized by descriptive statistics for each dose group for idronoxil alone on Days 1 and 7. Graphical methods may be used to assess the relationship between idronoxil and doxorubicin concentrations and QTc values and other toxicities of interest.

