14.3.11 QUALITY OF LIFE

All Quality of Life (QoL) analyses will be performed on the FAS. Scales from the EORTC-QLQ-C30 and items from the Brief Pain Inventory – Short Form, EORTC-QLQ-FA12 and Suppository Acceptance Questionnaire at each time point and changes from baseline will be summarized using descriptive statistics. Details of the scoring algorithms used to generate the QoL scores will be described in the SAP.

A Statistical Analysis Plan (SAP) will be developed and the analysis will be performed by a statistician using SAS {version TBD}.

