22.2.2 PHARMACOKINETIC, PHARMACODYNAMIC SAMPLES AND ELECTROCARDIOGRAPHIC TIMEPOINTS

22.2.2.1 Collection for Plasma Pharmacokinetic Samples

Blood samples for idronoxil and doxorubicin will be taken by venipuncture or cannula at time points detailed in Sections [11.4.3](#) and [22.2.2.2](#). Pre dose samples should be collected within 15 minutes prior to dosing. The sampling times for collection of blood for analysis of idronoxil, its metabolites, doxorubicin and doxorubicinol are listed in [Table 7](#).

Table 7 Pharmacokinetic Sampling Times for NOX66 and Doxorubicin

Monotherapy and Cycle 1

Cycle \ Day	D 1	D 2	D 7	Day 8	C1D2		C1D7	C1D8
Hours Post Dose	Monotherapy ^e				NOX	Dox	NOX	NOX
Pre-Dose	X	X	X		X ^d		X ^g	
0.5						X ^f		
1	X		X		X ^e			
2	X		X		X ^e			
3	X		X					
4	X		X		X ⁱ	X ^f		
6	X		X		X ⁱ	X ^f		
8	X		X	X ^b				X ^{b,e}
12				X ^c				X ^{c,e}

See footnotes on table below.

Cycle	C2		C3				C4		C5				C6	
Day	D2		D2		D7	D8	D2		D2		D7	D8	D2	
Hours Post Dose	NOX	Dox	NOX	Dox	NOX	NOX	NOX	Dox	NOX	Dox	NOX	NOX	NOX	Dox
Pre-Dose	X ^h				X ^g		X ^h				X ^g		X ^h	
0.5		X ^f						X ^{fi}						X ^f
1														
2														
3														
4	X	X ^f	X				X	X ^f	X				X	X ^f
6														
8						X ^{b,e}						X ^{b,e}		
12						X ^{c,e}						X ^{c,e}		

Samples for idronoxil are to be collected in Potassium Oxalate/Sodium Fluoride containing tubes.

^b Only for TID - 8 hours after the last dose of NOX66 on Day 7

^c Only for BID - 12 hours after the last dose of NOX66 on Day 7

^d Pre dose of NOX66

^e Only for Dose Escalation Cohorts

^f PK sample for Dox

^g Prior to last morning dose of NOX66

^h Prior to the morning dose of NOX66 administration (8 or 12 hours after the last dose of NOX66 on Day 1).

ⁱ Only for Dose Expansion Cohort

The following PK samples can be obtained at the patient's home if needed: 1) 24-hour sample on Day 1 of Monotherapy period, 2) Day 1 of the Washout Period (8 or 12 hours after the last dose, of a TID or BID, dosing regimen, respectively) on Day 7 of Monotherapy period], 3) pre-dose Day 7 and at 8 or 12 hours after the last dose on Day 7 of a TID or BID, dosing regimen, respectively for Cycles 1, 3 and 5.

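### After Cycle 2, 1800 mg/day patients may change from 600 mg TID to 600 mg morning plus 1200 mg evening, but the stated summaries do not separate the two schedules in late acceptance scores and pre-dose troughs

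*Combined protocol and SAP*

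**What the plan says.** Table 1 in Section 10.2.1 makes 1800 mg/day the only TID level; 800 and 1200 mg/day are given BID. Section 10.2.1 then allows patients who have trouble with TID dosing, for any personal reason, to move to twice-daily dosing after Cycle 2: "patients can administer one 600-mg suppository in the morning and two 600-mg suppositories in the evening". It also requires that "The dosing time for each suppository must be recorded by the patient in a diary".

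The analysis sections group the data as follows.

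- Section 14.3.1: "All data will be summarized by idronoxil dose group".
- Section 14.3.9: "Blood concentration of idronoxil and metabolites will be summarized by collection time for each dose group using descriptive statistics". It adds trough assessments on Days 7 and 8 of Cycles 1, 3 and 5, and a comparison of idronoxil levels alone and with doxorubicin.
- Section 14.3.11: "Suppository Acceptance Questionnaire at each time point and changes from baseline will be summarized using descriptive statistics". It does not mention dose group; that comes from the general rule in 14.3.1.
- Section 14.3.3 counts changes in idronoxil and doxorubicin doses. It does not mention changes of schedule.
- Section 11.1.2.1, on the combination-cycle samples: "Comparisons will be made to assess the degree of inter-and intra-patient variability during the study".

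Table 7 in Section 22.2.2.1 has a single pre-dose row. Its footnote for Day 2 of Cycles 2, 4 and 6 reads: "Prior to the morning dose of NOX66 administration (8 or 12 hours after the last dose of NOX66 on Day 1". The synopsis says that the recommended Phase 2 dose may be defined partly by whether the dosage form, dosing frequency included, is acceptable to patients.

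**The concern.** As first assigned, dose group separates the schedules: BID at 800 and 1200 mg, TID at 1800 mg. The option in 10.2.1 breaks that link inside the 1800 mg group, and no stated summary uses the schedule actually taken.

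Acceptability matters more, because the switch is selective. The patients allowed to leave TID are those who find it difficult. Each such switch is evidence against TID, yet the patient's later scores rate an easier schedule and would be reported under 1800 mg. If the switch does not appear in the exposure summary either, a reader of the results sees late 1800 mg scores with no sign that some concern a different frequency.

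For the troughs, a change of schedule could be taken for intra-patient variability, or for a difference between monotherapy and combination in later cycles.

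**Working it through.** The plan states no figure on this point to reproduce. The check has three steps.

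**1. Does a switcher stay in the same group?** Before: 3 × 600 = 1800 mg/day. After: 600 + 1200 = 1800 mg/day. The dose group is unchanged, and the daily dose gives no reason to count a dose change under 14.3.3.

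**2. Which observations can be affected?** From the visit schedule (11.6.2 and Table 4) and Table 7, for a patient who switches at Cycle 3 and completes six cycles:

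| Item | All planned | Possibly after a switch |
|---|---|---|
| Combination-cycle pre-dose idronoxil samples | C1D2, C1D7, C2D2, C3D7, C4D2, C5D7, C6D2 = 7 | C3D7, C4D2, C5D7, C6D2 = 4 |
| Acceptance questionnaires, escalation | monotherapy Day 7, C2D1 to C6D1, C6D21 = 7 | C4D1, C5D1, C6D1, C6D21 = 4 |
| Acceptance questionnaires, expansion | C2D1 to C6D1, C6D21 = 6 | the same 4 |

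The C3D1 questionnaire still rates Cycle 2 on TID. If 1800 mg is the MTD, at most 6 + 16 = 22 planned patients are exposed to the option. Day 8 samples have separate 8 h and 12 h rows, so collection time can distinguish them.

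**3. How far could a trough move?** The documents give no half-life, absorption rate or switch rate, so all three are assumptions here. The model is one-compartment superposition from Day 1 of a cycle, without carry-over. With immediate absorption, each earlier dose D contributes D × 2^(−t/h), where t is hours since that dose and h is the half-life. TID is 600 mg at 0, 8 and 16 h each day; switched is 600 mg at 0 h and 1200 mg at 12 h.

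Example, h = 4 h, pre-dose on Day 2 (24 h):

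- TID: 600 × (2^−2 + 2^−4 + 2^−6) = 150 + 37.5 + 9.4 = 196.9
- Switched: 1200 × 2^−3 + 600 × 2^−6 = 150 + 9.4 = 159.4
- Ratio: 159.4 / 196.9 = 0.81. Day 7 (144 h) gives 161.9 / 200.0 = 0.81.

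For first-order absorption, each term becomes D × ka/(ka − k) × (e^(−kt) − e^(−ka·t)), with k = ln 2 / h. Switched/TID ratio of the Day 7 pre-dose level:

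| Assumed half-life | Immediate | ka 0.7/h | ka 0.3/h |
|---|---|---|---|
| 2 h | 0.47 | 0.49 | 0.72 |
| 4 h | 0.81 | 0.82 | 0.92 |
| 8 h | 0.95 | 0.95 | 0.99 |
| 12 h | 0.98 | 0.98 | 1.01 |

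Group mean shift = share switched × (ratio − 1). With an assumed 25% switching and immediate absorption, 2 h gives 0.25 × (0.473 − 1) = −13%; 4, 8 and 12 h give −5%, −1% and −0.5%. With ka 0.3/h the four shifts are −7%, −2%, 0% and 0%. The effect is material only for a half-life of about 4 h or less, and smaller if absorption is slow.

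**The case against.** The strongest reply is that this is detail the protocol defers. Section 14.3.12 leaves presentations and data-handling rules to an SAP to be approved before the expansion cohort opens, and 16 of the 22 patients at issue would enrol after that. The diary records every dosing time, so nothing is lost and the schedule can be derived at analysis. Section 11.1.2.1 also lets the sponsor exclude non-evaluable concentrations with documentation. All of this stands. It shows that the remedy is easy, not that the plan commits to it: the grouping rule as written would put both schedules together.

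A reader might infer that the recommended Phase 2 dose is compromised. The documents do not support that. The synopsis wording is permissive, Section 8.3.6 mentions only the dosage form and not its frequency, and no score, time point or threshold is set. Three TID-only questionnaires in escalation (two in expansion) also precede any switch.

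A reader might likewise infer a material bias in the pharmacokinetics. The synopsis describes the combination-cycle sampling as intended "to assess variability of exposure of idronoxil and doxorubicin in an exploratory manner". The analysis is descriptive, and the calculation allows a shift near zero.

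Finally, an increase in the evening administration from 600 to 1200 mg can be read as a dose change under 14.3.3. So a switch need not be counted there, but it cannot be said that it would go unreported.

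**Conclusion.** The point holds, as a limited one. Section 10.2.1 creates two schedules inside the 1800 mg group, and the stated summaries do not separate them. The acceptability consequence needs no pharmacokinetic assumption: late scores would mix two schedules and could overstate TID acceptability, because difficulty with TID is the reason for switching. The trough consequence is exploratory and of unknown, possibly negligible size.

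Both depend on 1800 mg being reached and on patients switching and staying on treatment into the later cycles; the documents give no switch rate. The option opens only after Cycle 2, so the DLT window, the MTD decision, the monotherapy parameters and all Cycle 1 and 2 samples are unaffected. Nothing in the documents shows a harm that would call for separate adverse-event listings after a switch. The change is a cheap improvement.

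**What to change.** In Section 14, or in the SAP due before expansion opens:

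1. Derive a regimen flag for each patient and cycle from the dosing diary.
2. Report the number of switchers and the cycle of switch in the 14.3.3 exposure summary, and again beside the acceptability results. Separating the scores is not enough, since those who remain on TID are the ones who manage it; the count of those who left must be read with them.
3. Present post-switch acceptance scores and pre-dose troughs separately from 600 mg TID, as an individual listing if there are few.
4. Leave post-switch troughs out of the intra-patient variability and monotherapy-versus-combination comparisons.

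The cost is one derived variable and a few sentences, with no new samples or visits. The downside is smaller late-cycle numbers under 600 mg TID.

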10.2.2 DURATION OF THERAPY

In the Dose Escalation part of the study, the duration of therapy for NOX66 alone is one week. After an off-treatment for 5 days, combination therapy with doxorubicin will be initiated and on Day 1 of Cycle 1, NOX66 will be administered at the same dose level as in the Monotherapy period. Doxorubicin (75 mg/m²) will be administered on Day 2 of Cycle 1. This is followed by an off-treatment period of 2 weeks and then Cycle 2 will be initiated in the same manner as

for Cycle 1. Up to 6 cycles of doxorubicin can be administered and up to 7 weeks of NOX66 can be administered during this study.

For the Dose Expansion Cohort, patients will enter Cycle 1 of combination therapy and receive NOX66 for 7 days and on Day 2 they will receive doxorubicin. This will be followed by a 2-week rest period before starting the next cycle with a maximum number of 6 cycles.

10.2.3 DOSE MODIFICATIONS

The dose of doxorubicin can be reduced from 75 to 60 mg/m² if a Grade 2 toxicity related to doxorubicin occurs. If serum bilirubin is 1.2-3.0 mg/dL prior to a cycle, a 50% dose reduction of doxorubicin is recommended. If serum bilirubin is 3.1-5.0 mg/dL prior to a cycle, a 75% dose reduction of doxorubicin is recommended.

If a perineal and/or anal rash develops (Grade 1-2), a topical hydrocortisone containing haemorrhoid cream/ointment and/or cutaneous cream should be used. For Grade 3-4 perineal and/or anal rash, NOX66 treatment should be delayed until the rash resolves to Grade 1 or completely. NOX66 should also be delayed if there is proctitis, rectal mucositis, or ulcer of Grade 2 or higher. Treatment may be resumed when toxicity decreases to Grade 1. Treatment with NOX66 should also be delayed in the presence of anorectal infections and may be resumed after they are resolved.

All dose delays for NOX66 and doxorubicin need to be discussed with the Medical Monitor.

For patients developing neutropenia, the following guidelines should be used for doxorubicin dose modification.

Toxicity	Recommended Dose Modification
ANC < 1,000	No doxorubicin administered; treatment cycle delayed
≥ Grade 3 neutropenic fever/infection	Approximately 60 mg/m ² doxorubicin
≥ Grade 4 neutropenia lasting longer than 1 week	Approximately 60 mg/m ² doxorubicin
Second incidence of either: 1) ≥ Grade 3 neutropenic fever/infection 2) Grade 4 neutropenia lasting longer than 1 week	Second dose reduction to 45 mg/m ²
Reversible Grade 3 neutropenia with fever/infection or Grade 4 ANC	Retreatment with doxorubicin at Investigator's discretion

Abbreviation: ANC = absolute neutrophil count

In the event of cardiac toxicity (e.g., if there is an absolute decrease in LVEF of >10% from the previous evaluation, or if the actual LVEF decreases to ≤40%) doxorubicin must be discontinued. Doxorubicin must also be discontinued if the patient develops Grade 3 or 4 left ventricular systolic dysfunction (symptomatic congestive heart failure).

Patients who discontinue doxorubicin after 4 cycles of treatment should complete the remaining 2 cycles of NOX66 as planned. If doxorubicin is discontinued prior to 4 cycles, NOX66 treatment may continue in consultation and agreement with the Medical Monitor.

